## 2 Study Methods

### 2.1 Study Design

Pilot Validation: This is a pilot validation study involving a comparative investigation of a commercially available tympanometer with a minimal risk lay-friendly (mHealth) tympanometer prototype. The pilot validation will be conducted in consented adults and children presenting to the Audiology Clinics of UAMS and AC. The study will evaluate device performance compared to a commercial tympanometer in patients with various middle ear pathologies. Data acquired from the pilot validation will also be used with our machine learning algorithm to determine how well it works with prototype data and the if there will be a need for further refinement.

Eligible patients will be invited to participate, and the consent form reviewed. Consented participants will receive their audiological services as scheduled, with the addition of prototype measurements to their appointment. The audiology appointment will include routine ear and hearing measures, such as otoscopy (visual ear exam) and pure tone testing. The prototype device will be conducted before the commercial tympanometry. Audiologists will be asked to complete the prototype measurement and interpretation prior to the commercial device to limit bias in study results.

The resulting tympanograms from the prototype device and the clinical tympanometer will be interpreted by the audiologist and entered in a secure Research Electronic Data Capture (REDCap) database. The audiologist will also answer a few brief questions after testing each participant in a REDCap form on device performance for both the prototype and commercial tympanometers.

Specifically, the order of events will be as follows:

1. Audiologist will test each ear of the participant with the prototype device and interpret the tympanogram. These findings will be entered in a secure Research Electronic Data Capture (REDCap) database in real time using a tablet or computer.
2. Next, the audiologist will test each ear of the participant with a commercial tympanometer, interpret the results and enter them in the database as described above.
3. Finally, the audiologist will complete 4 questions on user experience with the prototype and commercial devices and document it in a secure REDCap database.

Testing the machine learning algorithm: The performance of the machine learning algorithm will be tested by using raw data from the prototype mHealth tympanometer obtained from the pilot validation study. The ML will interpret the raw tympanometric data and classify the results into Type A, B, and C. The classification by the ML algorithm will be compared to audiologists' interpretation, and concordance will be assessed. The audiologists interpreting the data will be blind to the ML algorithm, and the ML algorithm interpretation will not be provided the audiologist.

### 2.2 Power and Sample size

A sample size of 30 participants (60 ears), with an assumed prevalence of 0.20 will yield a half-width of 95% confidence interval ranging from 0.25-0.33 when the sample sensitivity is 0.80; and a half-width of 95% confidence interval ranging from 0.12-0.18 when the sample specificity is 0.80. The range of the half-width of 95% confidence interval reflect the extreme scenario of the intra-class correlation ranging from 0 to 1.

### 2.3 Sampling Strategy

Convenience sampling will be employed for this study. We will recruit a minimum of 30 participants, which will include adults (n=20) presenting to the Audiology Clinic of University of Arkansas for Medical

Sciences (UAMS) and pediatric participants (n=10) presenting to Arkansas Children's (AC) Audiology Clinic. In total, a minimum of 60 ears will be included in the analysis.

## 2.4 Study Population

Adult and pediatric patients presenting to audiology clinics of UAMS and AC with various middle ear pathologies.

## 2.5 Inclusion Criteria

### Audiology Patient Participants

- Individuals, 1-year and older
- Presenting to the UAMS or AC Audiology Clinics for evaluation where tympanometry is warranted for testing at the discretion of the audiologist (current practice).
- Presence of various middle ear health states/pathologies that result in Type A, B, C tympanograms; examples include normal, occluding cerumen, effusion, perforation, retraction otosclerosis, cholesteatoma, ossicular chain discontinuity, myringitis, and tympanosclerosis
- English-speaking

## 2.6 Exclusion Criteria

- Children or adults with cognitive disabilities
- Unable to provide consent/assent
- Individuals who are unable to sit still
- Any other condition, that, in the opinion of the investigator, might interfere with the safe conduct of the study or place the participant at increased risk

## 2.7 Data Acquisition

Table 1. Data acquisition

Study design	Pilot validation study
Data source/how the data were collected	
REDCap Survey: Link will be added later
 
Data collected during study visit:
 

• Enrollment form

• Data collection form

◦ Audiologist Otoscopy Interpretation

◦ Audiologist Interpretation and Performance for prototype device

◦ Audiologist Interpretation and Performance for commercial tympanometer

• ML Algorithm Interpretation form

Contact information for team member responsible for data collection/acquisition	
Date or version (if downloaded, provide date)	
Data transfer method and date	
Where dataset is stored	REDCap

### 3 Analysis Population

The analysis population will consist of all subjects who are enrolled in the study and on whom both the study devices have been administered.

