Eligible patients will be invited to participate, and the consent form reviewed. Consented participants will receive their audiological services as scheduled, with the addition of prototype measurements to their appointment. The audiology appointment will include routine ear and hearing measures, such as otoscopy (visual ear exam) and pure tone

Title: "Pilot Validation of a Prototype Mobile Health Tympanometer"
PI: [name], MPH
Institution: University of Arkansas for Medical Sciences

testing. The prototype device will be conducted before the commercial tympanometry. Audiologists will be asked to complete the prototype measurement and interpretation prior to the commercial device to limit bias in study results. We anticipate approximately 3 audiologists from UAMS and 2 audiologists from AC being involved in the study. Audiologists will be provided initial training and a demonstration of the prototype device and given instruction on how to troubleshoot and who to contact should an unanticipated problem occur. The tympanometric measurement takes roughly 10-15 seconds per ear to collect. We anticipate the prototype measurement and data entry will take no more than 5 minutes to complete during the audiological appointment.

The resulting tympanograms from the prototype device and the clinical tympanometer will be interpreted by the audiologist and entered in a secure Research Electronic Data Capture (REDCap) database. The audiologist will also answer a few brief questions during/after testing each participant in a REDCap form on device performance for both the prototype and commercial tympanometers.

Specifically, the order of events will be as follows:

1. Audiologist will test each ear of the participant with the prototype device and interpret the tympanogram. These findings will be entered in a secure Research Electronic Data Capture (REDCap) database in real time using a tablet or computer.
2. Next, the audiologist will test each ear of the participant with a commercial tympanometer, interpret the results and enter them in the database as described above.
3. The audiologist will complete 4 questions on each device performance between testing with each device (steps 1 and 2) if time permits, or after completion of testing with both the devices, and document it in a secure REDCap database.

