- Possible - The AE may be related to study treatment. The AE onset occurs in a plausible time relationship to study treatment; though, other factors (e.g., concurrent disease or concomitant medications/treatments) may have contributed to it.
- Unlikely - The AE is doubtfully related to study treatment. The AE onset does not occur in a plausible time relationship to study treatment, and other contributing factors (e.g., concurrent disease or concomitant medications/treatments) are likely.
- Unrelated - The AE is clearly NOT related to study treatment. There is not a causal relationship between the AE and the study treatment.

Expectedness

Unexpected AEs are those not listed in the device manual, protocol, or not identified. This includes AEs for which the specificity, nature, intensity, severity, incidence, or frequency is not consistent with the description in the device manual or protocol.

Study Period

Following consent, baseline/pre-existing conditions will be recorded and assessed until initiation of use of the study intervention. All AEs will then be recorded and assessed from the time of the initiation of study intervention through the end of the study visit in AE Case Report Forms. All AEs will be documented in the participant record (captured in source documents, including but not limited to the electronic medical record).

Monitoring, Recording, and Reporting of AEs

All participants will be monitored for AEs (serious and non-serious) during their participation in the study. AE data collection and reporting, which are required as part of every study, are done to ensure the safety of participants enrolled in the studies and those who will enroll in future protocols.

All AEs occurring during the study period whether volunteered by the participant; discovered by study personnel during questioning; or detected through physical examination, observation of clinical symptoms, laboratory, pathological, radiological, or surgical findings, or other appropriate means must be recorded and reported appropriately. AEs are to be reported in a routine fashion and at scheduled times during the study. Certain AEs must be reported in an expedited fashion to allow for timely monitoring of participant safety and care.

Pre-existing Conditions

A pre-existing medical condition is any condition, laboratory abnormality, or physical finding with an onset date at the start of the study (prior to the initiation of the use of any

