A change to, or non-compliance with, the IRB-approved procedures without prior Sponsor and IRB approval (excluding changes made to eliminate apparent immediate hazard to participants). A violation may affect health, safety, or rights of a participant. Any violation will be reported immediately to the Sponsor for guidance on reporting.

If the protocol deviation/protocol violation does not represent a significant alteration in the approved protocol and/or affect the safety or welfare of the participant, it will be reported to the UAMS IRB at the time of Continuing Review. If the protocol deviation/violation represents a significant alteration in the approved protocol and/or if it affects the safety or welfare of the participant, it must be reported to the Sponsor and UAMS IRB immediately.

Study Stopping/Pausing

This study is low risk, and no adverse experiences are anticipated. The device is being designed with adherence to all the safety considerations established in IEC 60645-5. Each device will be labeled with a unique identifier that will correlate with specific hardware and firmware versions to allow performance and any adverse events to be recorded and a full root cause analysis (RCA) to be performed. If there are concerns during measurement such as discomfort reported by the patient, or device malfunction reported by the clinician, testing will be stopped immediately. The issue will be documented, reported to the PI, and the device will no longer be used until a full RCA has been performed. If this issue can be resolved immediately, then testing will be restarted with the participant. If the issue cannot be resolved immediately (i.e., within the duration of the clinical appointment), then the data will be considered incomplete and additional participants will be recruited in order to meet recruitment goal of 40 adult ears with complete data and 20 child ears with complete data. The participant will still receive the \$20 gift card. While both ears will be tested, if data can only be obtained in one ear, the participant will still be considered to have completed the study as long as results from both the devices can be obtained for that ear. Any safety concerns will be reported to the PI, ORRA, and the UAMS IRB. Any event related to changes in consent form, protocol, or inadvertent disclosure of confidential information will be reported to the IRB.

Data Analysis

Pilot Validation Analysis

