### **5.6 Safety Analysis**

Adverse events (AE) constitute any untoward or unfavorable occurrence in a research participant associated with the participant's involvement in the research that may or may not be related to the individual's participation in research. The adverse events will be collected and coded in accordance with the guidelines specified in MedDRA/CTCAE.

Serious adverse events (SAE) refer to the adverse events that meet at least one of the following criteria:

- Leads to death
- Considered life threatening (putting participants in immediate risk of death)
- Necessitates inpatient hospitalization or prolongation (if already hospitalized)
- Results in persistent or significant disability/incapacity
- Requires medical or surgical intervention to prevent outcomes listed in the above definition of SAE
- Causes significant psychological, social, economic, or legal harm to participants or others
- Results in breach of confidentiality that is damaging to participants' rights, employment, financial standing or reputation

Adverse events will be analysed and listed as per the guidelines listed below:

1. If a participant experiences the same AE multiple times during the study, the patient will be counted only once in the number of participants experiencing the event.
2. If a patient experiences the same AE multiple times but with different severity during the study, the worst or most intense event will be counted.
3. If there are adverse events that are not coded, the summary table will use the exact description from as reported in the database. The statistician may consult with the study investigator for further information to resolve this (i.e. whether it can be reassigned to one of the existing coding)

The safety analysis will be descriptive, and no inferential statistics will be done. Summary statistics will be presented by severity and device relatedness.

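### The SAP's only analysis population requires both devices, and the AE summary names no other set, so a participant exposed to the prototype alone would be left out of it

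*SAP*

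**What the plan says.** SAP section 3 gives one definition and no alternative: "The analysis population will consist of all subjects who are enrolled in the study and on whom both the study devices have been administered". Intent-to-treat and per-protocol appear in the SAP's acronym list but are neither defined nor used, and no safety set is listed.

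SAP section 5.6 describes the AE analysis as descriptive. It counts a participant once per event, takes the worst severity, and adds that "Summary statistics will be presented by severity and device relatedness". It does not say which participants form the numerator or the denominator.

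On test order, the protocol (Study Design and Procedures) states: "The prototype device will be conducted before the commercial tympanometry". SAP section 2.1 says the same.

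The protocol's Study Stopping/Pausing section provides that, for concerns such as "discomfort reported by the patient, or device malfunction reported by the clinician, testing will be stopped immediately". If the issue cannot be resolved within the appointment, "then the data will be considered incomplete and additional participants will be recruited in order to meet recruitment goal".

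On safety data, the protocol (Monitoring, Recording, and Reporting of AEs) says: "All participants will be monitored for AEs (serious and non-serious) during their participation in the study". Its Study Period section starts AE recording when the study intervention begins, with no condition that the commercial test follows.

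**The concern.** A safety denominator should hold everyone exposed to the investigational device. Here the only defined set is narrower: it also requires the comparator device, which always comes second. A participant whose prototype test ends early and who then does not have the commercial test has been exposed, may have had a device-related event, and does not meet the section 3 condition. Membership of the population can then depend on the safety outcome itself.

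The SAP calls the study first-in-human, and the protocol says that it will support an application for a larger validation study. With about 30 participants, one or two missing events would visibly change the reported AE frequency.

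**Working it through.** The plan states no AE rate, so there is no figure to reproduce. The check is a reading of the text followed by an illustration.

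**Reading the text**

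1. SAP section 3: membership requires enrolment and administration of both devices.
2. SAP section 5.6: no population is named, so section 3 supplies the only one.
3. SAP section 5.9: the complete-case rule covers the study objectives. Safety is not among Objectives 1 to 4, so this rule neither causes nor cures the gap.
4. Protocol and SAP section 2.1: the prototype comes first, so exposure to the prototype alone is possible.
5. Protocol, Study Stopping/Pausing: testing may stop during the prototype measurement. The text does not say whether the stop extends to the commercial test.
6. Protocol, Study Period: an event in such a participant is still recorded. The data exist, but the SAP has no analysis set that contains them.

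**Direction of the error**

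Let x of n participants with both devices have an AE, and a of e prototype-only participants have one. The section 3 population gives x/n; all exposed gives (x + a)/(n + e). The first is the smaller exactly when a/e > x/n. So the error is downward if prototype-only participants have AEs more often than the others, as expected when an event ended the test. If the commercial test was missed for an unrelated reason and there was no AE, the error runs slightly the other way.

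**Size, on assumed counts**

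Inputs: n = 30, the enrolment goal in the protocol's Data Analysis section. Assumptions, not figures from the documents: x = 0, a = e, and e as shown. Intervals are exact (Clopper-Pearson) 95%: the lower limit is the 0.025 quantile of Beta(k, N − k + 1) and the upper limit the 0.975 quantile of Beta(k + 1, N − k), for k events in N.

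Section 3 population: 0/30, upper limit 1 − 0.025^(1/30) = 11.6%, whatever e is.

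| Assumed e | All exposed | Proportion | 95% CI |
|---|---|---|---|
| 1 | 1/31 | 3.2% | 0.1 to 16.7% |
| 2 | 2/32 | 6.3% | 0.8 to 20.8% |
| 3 | 3/33 | 9.1% | 1.9 to 24.3% |
| 5 | 5/35 | 14.3% | 4.8 to 30.3% |

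These rows are deliberately one-sided: every prototype-only participant has an AE and nobody else does. They show how sensitive a table of this size is and do not forecast what will happen.

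**The case against.** The strongest reply is that the exclusion is inferred. Section 5.6 does not cite section 3, speaks of AEs as recorded in the database, and could be read as covering all of them. The table shells, which may state denominators, are in a separate document. This stands as a limit on the claim. It does not close the gap, because a plan with one population and no stated exception leaves the choice to whoever builds the table.

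The second reply is that the trigger is narrow. Eligibility requires that tympanometry is warranted clinically, participants receive their scheduled services, and section 3 asks only that the device was administered, not that a reading was obtained. A participant whose prototype test stops and who then has the clinical test stays in the population. This also stands, and it is why the number affected is probably small.

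Several stronger readings are tempting and are not supported:

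- *Every prototype test stopped for discomfort disappears from the AE table.* Stopping alone excludes nobody; only a missing commercial test does. The incomplete label in Study Stopping/Pausing concerns the ear-count goal, not the AE record.
- *Only prototype events can cause the loss.* A commercial test could also be missed through lack of time, an uncooperative child or withdrawal.
- *The SAP contradicts the protocol's AE monitoring.* The protocol governs collection and the SAP governs analysis. The two differ in scope, but both can hold.
- *Up to 10 exposed participants could be lost.* That takes 40 consented minus the goal of 30. The protocol explains a possible need for more than 30 participants by failure to obtain tracings. Such people may have had both devices applied, and consent is not exposure.
- *Safety oversight is weakened.* AE recording, Medical Monitor review and reporting to the sponsor, IRB and FDA do not use the SAP population.

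**Conclusion.** The point holds in a limited form. Followed literally, SAP sections 3 and 5.6 leave a participant exposed only to the prototype out of the AE summary, and that exclusion can depend on a prototype event. When it does, the reported AE frequency is too low: 0/30 instead of 2/32 = 6.3% under the two-participant assumption.

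The conclusion rests on section 3 governing section 5.6 by default and on at least one participant not going on to the commercial test. The documents give no basis for estimating how many that would be. The effect is confined to a descriptive table. Severity is minor: a cheap improvement to make before the analysis.

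**What to change.** In SAP section 3, add a safety population: all enrolled participants in whom prototype testing was started or attempted in at least one ear, whether or not a reading was obtained or the commercial device was used. In SAP section 5.6, state that AE counts and denominators use this population. Keep the both-devices population for the accuracy and agreement objectives.

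The cost is two sentences. No new data are needed, since the protocol already records AEs from the start of the study intervention, and clinical conduct does not change. The reported AE rate may become slightly less favourable.

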### 4 Outcomes, Exposures, and Additional Variables of Interest

#### 4.1 *Outcome(s)*

Table 2. Description of outcome variables

Outcome	Description	Variables and Source	Specifications
Primary Outcome(s)			
Categorical classification of tympanogram types A, B, C  1) Audiologist's interpretation of commercial device versus audiologist's interpretation of prototype device  2A) Audiologist's interpretation of prototype device versus machine learning algorithm's interpretation of prototype device  2B) Audiologist's interpretation of commercial device versus machine learning algorithm's interpretation of prototype device	Tympanograms can be classified into types (Type A, B, C) that help to determine if an eardrum has fluid behind it, is retracted, or perhaps has a perforation, all common ear disease states. Type A indicates normal ear function, and types B and C indicate abnormal middle ear function.	Audiologist commercial device classification (left, right): Tymp_type_au_com_l; Tymp_type_au_com_r  Audiologist prototype device classification (left, right): Tymp_type_au_proto_l; Tymp_type_au_proto_r  Machine learning algorithm prototype device classification (left, right): Tymp_type_ml_proto_l; Tymp_type_ml_proto_r  Forms: 1) Data collection form: Audiologist interpretation and performance for mHealth tympanometer  2) Data collection form: Audiologist interpretation and performance for commercial tympanometer  3) ML Algorithm Interpretation form	1=A; 2=B; 3=C; 4=CNE (could not evaluate)
Secondary Outcome(s)			
Ear canal volume, static admittance and	Numerical measures	Commercial device (left, right):	Numerical measures

tympanometric peak pressure	Commercial device versus prototype device	
ecv_com_l; sa_com_l; tpp_com_l; ecv_com_r; sa_com_r; tpp_com_r
 
Prototype device (left, right): ecv_proto_l; sa_proto_l; tpp_proto_l; ecv_proto_r; sa_proto_r; tpp_proto_r
 
Forms: 1) Data collection form: Audiologist Interpretation and Performance for commercial tympanometer  2) ML Algorithm Interpretation form

Device performance	
Device performance will be evaluated using a 4-item 5-point Likert scale survey
 
Prototype device performance: perform_proto_Q1 perform_proto_Q2 perform_proto_Q3 perform_proto_Q4
 
Commercial device performance: perform_com_Q1 perform_com_Q2 perform_com_Q3 perform_com_Q4
 
Forms: 1) Data collection form: Audiologist Interpretation and Performance for mHealth tympanometer  2) Data collection form: Audiologist Interpretation and Performance for
	
1=Completely disagree; 2=Disagree; 3= Neither Agree nor Disagree; 4=Agree; 5=Completely Agree

		commercial tympanometer	
--	--	----------------------------	--

